### **Visit 2**

Baseline Testing/1st Run-in SHAM stimulation visit (Approx Time: 1  $\frac{1}{4}$  hours)

*The first baseline testing might be completed on the same day as the screening visit if time allows and the subject agrees.*

There will be 2 SHAM stimulation visits to be completed approximately 48 hours apart over about one week (this visit will include the first SHAM stimulation session). The subject will receive 20 minutes of SHAM tDCS in conjunction with SHAM TUS.

Before SHAM stimulation, the subject will complete the following assessments:

- Urine pregnancy exam (if applicable)
- Visual Analog Mood Scale (VAMS)
- Mini Mental State Examination (MMSE)
- Neurological and Physical Exam
- Visual Analogue Scale (VAS) for Pain
- Pain/Medication Diary
- EEG recording
- NIH CLBP RMD instrument
- 29-PROMIS short form
- Beck Depression Inventory (BDI)

After SHAM stimulation subjects will complete the following assessments:

- Adverse Events (AE)

- Visual Analogue Scale (VAS) for Pain
- Screening Form for Part II

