#### *Blinding:*

All subjects and investigators will be blinded to the group assignment except for the co-investigators providing stimulation and staff involved in the randomization process (the latter would otherwise not be involved in study procedures). Only the staff involved in the randomization will be authorized to break the blind if there is a clinical need as requested by the PI, clinical care providers, Medical Monitor, or IMC. The patients will remain blinded until they have completed all visits (whether they complete all 23 visits or drop out early), or in the case of an adverse event necessitating un-blinding.

If the subject receives sham stimulation during Part II, he/she may re-enroll into an open label portion of the study, where he/she will receive 10 days of active tDCS/TUS. Un-blinded co-investigators (e.g., who provided stimulation) will coordinate with subjects electing to enter into the open label phase, which will be conducted by the un-blinded study staff. In the open label phase, we will complete the VAS assessments on Day 5 and Day 10 of stimulation. This

collected data will not be analyzed with the main data collected in the study. This data will be used for exploratory analyses only.

After stimulation subjects will complete the following assessments:

- Visual Analog Mood Scale (VAMS)
- Mini Mental State Examination (MMSE)
- Stroop test
- Neurological and Physical Exam
- EEG recording \*
- Adverse Events (AE)
- Visual Analogue Scale (VAS) for Pain

\* *The EEG can be performed at anytime during the first week of stim (V4b-V8).*

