*Adverse Effects Questionnaire:* At each session after stimulation begins, subjects will complete a questionnaire to evaluate potential adverse effects of stimulation (headache, neck pain, mood alterations, and seizures) on a 5-point scale. The scale will also be administered at the follow-up. The subjects will be asked whether they have experienced any side effects in an open-ended manner and they will then be specifically asked about headache, neck pain, scalp pain, scalp burns, tingling, skin redness, sleepiness, trouble concentrating, and acute mood change. If any side effects are reported, the degree of relatedness to the intervention will be assessed.

[figure not shown]
We will be investigating adverse effects using open-ended questions. An AE can be any unfavorable and unintended sign, symptom, or disease temporally associated with the use of a treatment, whether or not considered related to the product.

Examples of AEs are as follows:

- Subjective symptoms offered by or elicited from the subject
- Objective signs observed by the Investigator or other study personnel

All concurrent diseases that occur after the start of the study, including any change in severity or frequency of preexisting disease will be investigated in several domains including: seriousness, severity, length of duration, and if any causal relationship exists with the intervention [53].

*Walking Test:* Patients will be asked to walk at comfortable speed for 10 meters to assess gait patterns. Quantitative objective metrics of walking will be extracted from the recorded data such as walking speed, gait asymmetry, stride length, and walking smoothness [105-108].

*NIH CLBP RMD and PROMIS 29 instruments- Patients will fill out questionnaires are designed to assess the low back pain and the impact of pain on function, psychological, sleep, and related activities.* The NIH CLBP Research Task Force (RTF) Recommended Minimum Dataset (RMD) instrument is made of the components of the Patient Reported Outcomes Measurement Information System (PROMIS) instrument [116], the Subgroups for Targeted Treatment (STarT) Back instruments[117], and the RTF Impact classification (see NIH Research Task Force (RTF) for low back pain assessment recommendations [5]). Components of the 29-PROMIS short-form [116] not included as part of the NIH Minimum Data Set Instrument (e.g., elements of anxiety and fatigue) will also be assessed.

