#### **IV. BIOSTATISTICAL ANALYSIS**

Data forms and questionnaires will be coded in a standardized manner, and double-entered into our database. Digital measures/recordings will be similarly tracked in our database and regularly backed up. Analyses will be conducted using standard statistical software such as SAS and Matlab.

Sample size calculations and data analysis:

*Aim 1:*

For planning sample size calculation for this study, we considered the surrogate pain outcomes as the main outcome for such analysis; considering the two studies showing significant alterations of these outcomes in NSCLBP [118], an effect in the active tDCS in conjunction with active TUS that is twice of the effect in SHAM tDCS in conjunction with SHAM TUS would be adequate. Considering this effect size and a power of 80% and alpha of 5%, we would need 6 subjects per group for a total of 12 subjects. Therefore considering dropouts and also to increase the sample in phase I for the clinical outcome, we increased the sample to 20 subjects (10 for each arm), that would also give a power to detect significant differences of 2 points in VAS between the 2 groups; though the clinical outcome is not the main outcome in phase 1. For Phase 2, we doubled the sample size as to have enough power to detect a difference of 1.3 in VAS between the two groups that would therefore be adequate to demonstrate a clinically meaningful difference between the two groups. We considered differences smaller than that not clinically meaningful.

All analyses will be conducted according to the principle of intention-to-treat (using regression-based single imputation method). We will also perform an additional sensitivity analysis in

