which we will use the method of last observation carried forward. The primary outcome will be TS and CPM [118] (in phase 1) and VAS (in phase 2) changes as indexed by VAS scores, biomechanical function changes as indexed with the motion analysis suite, and global self-assessment changes. Differences between the two groups (active tDCS in conjunction with active TUS and SHAM tDCS in conjunction with SHAM TUS) will be tested using Student's t-test and, in addition, we will adjust for important baseline variables and also test the time effect in general mixed longitudinal models. This model will be used for the primary and secondary outcomes. Secondary analyses will be conducted in an exploratory manner (no correction for multiple comparisons). Similar analysis will be conducted for the adverse effects measuring continuous outcome and for the categorical outcomes we will use Fisher's exact test. In both cases, for safety analysis we will use uncorrected p-value to increase the likelihood of detecting detrimental adverse effects.

332-6.

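### Read literally, the imputation rule for all analyses also covers adverse-effect scores, so scores missing after a patient leaves would be filled in; safety should be exempted

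*Combined protocol and SAP*

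**What the plan says.** All the analysis wording is in section IV (Biostatistical analysis, Aim 1) of the combined protocol and SAP.

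- The general rule: "All analyses will be conducted according to the principle of intention-to-treat (using regression-based single imputation method".
- A sensitivity analysis is added, in "which we will use the method of last observation carried forward".
- After naming Student's t-test and adjusted mixed longitudinal models for efficacy, the section turns to safety: "Similar analysis will be conducted for the adverse effects measuring continuous outcome", and "for the categorical outcomes we will use Fisher's exact test".
- The purpose of the safety analysis is explicit: "for safety analysis we will use uncorrected p-value to increase the likelihood of detecting detrimental adverse effects".

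Under Description of assessments, at each session once stimulation has begun, "subjects will complete a questionnaire to evaluate potential adverse effects of stimulation". The answers are on a 5-point scale, and the scale is repeated at follow-up. The same entry provides for open-ended reporting of adverse events, with seriousness, severity, duration and causal relation.

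Missing scores are foreseeable. The Blinding paragraph speaks of patients "whether they complete all 23 visits or drop out early", and the end of Description of assessments allows any assessment except VAS pain to be skipped. No section exempts safety data from imputation, defines a safety population, or treats leaving because of harm separately.

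**The concern.** Imputation for an efficacy endpoint tries to estimate what would have been seen had the patient stayed. A safety analysis has a different purpose: to describe what patients experienced. If a patient stops after a bad reaction and later scores are predicted from a model fitted to those who remained, the filled-in values may describe tolerance that the patient did not have. Carry-forward has the opposite fault, since one short-lived symptom at the last attended session is then counted at every later visit. Neither set of values was observed.

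At stake is whether the continuous safety comparison serves the plan's own aim of making harm easier to detect. With 20 patients per arm, a few leavers are enough to move an arm mean.

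**Working it through.** **1. Scope.** The general rule covers all analyses. The adverse-effect analysis is an analysis, it is described as similar to one that uses the rule, and nothing removes it. The literal result is that missing continuous adverse-effect scores are imputed. For categorical adverse effects only the test is named; how a missing value enters it is not stated.

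**2. What is not specified.** The plan names no predictors for the regression and no visit or summary for the adverse-effect score. Run-in scores exist (Visit 2: "After SHAM stimulation subjects will complete the following assessments", with adverse events on that list) and could serve as predictors, as could a patient's own Part II scores. The plan gives no figure for the adverse-effect analysis, so there is none to reproduce.

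**3. Conditional arithmetic for one visit.** From the plan: 20 per arm (section III). Assumed: scale coded 1 to 5; stayers in the active arm average 1.5; k active patients have left; their unseen score would be s; the model fills in p.

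Understatement of the active-arm mean = k × (s − p) / 20.

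- p = 1.5, s = 4, k = 1, 2, 3, 4: 0.125, 0.25, 0.375, 0.5.
- p = 1.5, s from 3 to 5, k from 1 to 4: from 1 × 1.5/20 = 0.075 to 4 × 3.5/20 = 0.7.
- Symptom resolved after leaving, s = 1: k × (1 − 1.5)/20 = −0.025 to −0.1, so prediction then overstates harm.
- Regression that uses the patient's own last score of 4 with slope b (stayers again averaging 1.5): p = 1.5 + 2.5b. With s = 4 the understatement per leaver is (2.5 − 2.5b)/20, which is 0.125 at b = 0, 0.0625 at b = 0.5 and 0 at b = 1.

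**4. Simulation under one imputation model.** 4,000 trials per scenario; leavers all in the active arm with scores near 4, everyone else near 1.2; regression on intercept, run-in score and arm only. The true arm difference is k × (4 − 1.2)/20 = 0.14, 0.28, 0.42, 0.56 for k = 1 to 4. After imputation it is about 0.00 each time. For k = 4 the share of trials with p < 0.05 falls from 37% to 7%. This depends on leaving post-randomisation scores out of the model and on the unseen score staying near 4.

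**5. Carry-forward.** The visit lists include adverse effects at every visit from 7 to 23. For a patient who reports a symptom at Visit 6 and then leaves, that score is copied to Visits 7–19 (13) and 20–23 (4), 17 records in all. If the score was 4 and the symptom had gone (true score 1), the arm mean at each of those visits is overstated by (4 − 1)/20 = 0.15. If the symptom had persisted, the error is nil.

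**6. The categorical route.** Fisher's exact test, two-sided, k of 20 versus 0 of 20: p = 0.49, 0.23, 0.106 and 0.047 for k = 2, 3, 4, 5. An event recorded before leaving counts here without imputation, but the test needs about five events against none to reach 5%.

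**The case against.** The strongest reply is that the plan never says adverse-effect scores are imputed. The word for similarity follows the t-test and mixed-model sentences and may refer only to those. That is a fair reading of the one sentence, but it does not narrow the general rule, which reaches safety by itself. This part of the point remains a literal reading, not a declared intention.

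Other objections stand and limit the point:

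- A reader might infer that the scores of patients who leave are overwritten. The documents do not support that. Imputation fills missing values only, and because the questionnaire follows each session, an effect scored on that day stays in the data.
- A reader might set the worst recorded score beside an imputed last-visit score and conclude that imputation removes the whole arm difference. That contrast changes the summary as well as the missing-data rule. An observed-only last-visit comparison would also miss the leavers' harm, and the worst recorded score is not lowered by filling later visits with milder values. The plan does not specify a last-visit comparison.
- A reader might conclude that the safety result rests on the filling method instead of on observed events. That is too strong: Fisher's test and the open-ended adverse-event record use events as reported.
- Carry-forward is only the sensitivity analysis, and it keeps harm that was scored before leaving.

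**Conclusion.** The point holds as a conflict between a stated rule and a stated aim. As written, missing continuous adverse-effect scores would be predicted, or carried forward in the sensitivity analysis, in an analysis meant to raise the chance of seeing harm. Recorded scores are unaffected.

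No single magnitude can be given. The arm-mean error of 0.075 to 0.7 points rests on assumed coding, assumed scores, 1 to 4 leavers, and predictions at the stayers' mean. It shrinks to nothing if the model follows the patient's own last score and that score persists, and it reverses if symptoms resolve. The documents give no early-leaving rate, no predictors and no adverse-effect time point, so neither size nor direction is known. The categorical comparison is a real but partial safeguard at 20 per arm. The change is worth making because it is cheap and removes the dependence on an unspecified model; if the sponsor never meant to impute safety data, the same wording settles the ambiguity.

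**What to change.** Exempt safety from the general imputation rule in section IV, in wording to this effect:

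- No adverse-effect value is imputed or carried forward. The safety analysis uses observed data from all patients who received at least one Part II session.
- Each patient contributes the worst severity recorded after randomisation and a yes/no for each symptom. Stops because of adverse effects are tabulated by arm.

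The worst-severity summary is needed as well as the ban on imputation: observed-only analysis at a late visit would still lose patients who left.

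Cost: about two sentences and no new assessment, since the questionnaire is already scheduled at every Part II visit. The reason for each stop must be on record. One limit remains: a patient who leaves early has fewer visits at which a score can be recorded, so the table of stops should be read beside the severity comparison.

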### **III. STUDY PROCEDURES**

Because our protocol involves a run-in phase (Part I), we expect that up to 90 patients may enter the run-in phase so we will be able to randomize 40 eligible subjects to participate in this study (in phase II). When the target number of 40 subjects (for phase II) entering the randomized phase

(Part II) is completed, enrollment will end. Subjects who passed the run-in phase (Part I) successfully will then be randomly assigned to receive treatment in Part II with active tDCS+active TUS (n=20) or sham tDCS+sham TUS (n=20 inactive transducers).

**General Study Outline:** This two-Part study will consist of 23 visits over the course of about 15 weeks. After Visit 1, the remaining Part I of the study will take about a week (Visits 2-4a). Prior to any assessments, the subject will consent to participate in both Part I and Part II, pending that the subject fits the additional eligibility criteria\* of the run-in period. After completion of Part I, eligible subjects will continue onto Part II, the main interventional portion of the trial. Part II of the study will take place over the remaining weeks (Visits 4b-23).

*Part I Study Flow – Run-in Period (Visits 1-4a):*

- Screening Visit
- Run-in Visit 2&3 – sham stimulation visits
- Rescreening Visit

*Part II Study Flow – (Visits 4b-23):*

- 10 sessions of tDCS stimulation over 2 weeks
- Bi-weekly sessions of tDCS stimulation over 3 weeks
- 4 Follow-Up Visits – 2 week, 4 weeks, 6 weeks, and 8 weeks post-stimulation

Eligibility criteria for Part II include:

- VAS pain score greater than 1 following either of the two SHAM stimulation sessions [97] during Part I and pain reduction not greater than 72.52% (i.e. not a large placebo response)
- Stable pain intensities (defined as a difference in pain intensities less than or equal to 4 (on a 0-10 VAS scale) between the average over the week prior to visit 2 and the average over the week prior to visit 4a [96])
- High adherence during the Run-in stimulation visits (defined as completing both Run-in stimulation visits within approximately one week)
- VAS pain weighted average  $\geq 3$  prior to randomization during visit 4a (i.e. not exhibiting low baseline pain)

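### The plan does not say how up to 16 session ratings of adverse effects become one comparison per patient; if they are analysed as continuous, a brief severe effect would probably not show

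*Combined protocol and SAP*

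**What the plan says.** The Adverse Effects Questionnaire entry under Description of Assessments sets the timing: "At each session after stimulation begins, subjects will complete a questionnaire to evaluate potential adverse effects of stimulation". It is repeated at follow-up. The scale is attached to a short list: "headache, neck pain, mood alterations, and seizures) on a 5-point scale". After an open question, patients are also asked specifically about "headache, neck pain, scalp pain, scalp burns, tingling, skin redness, sleepiness, trouble concentrating, and acute mood change". That later sentence mentions no score. Concurrent diseases arising or changing after the study starts are examined for "seriousness, severity, length of duration, and if any causal relationship exists with the intervention".

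Section III gives the Part II schedule as "10 sessions of tDCS stimulation over 2 weeks" followed by "Bi-weekly sessions of tDCS stimulation over 3 weeks".

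In section IV, differences between arms "will be tested using Student's t-test", with a mixed longitudinal model in addition that adjusts for baseline variables and tests time. The safety sentence follows: "Similar analysis will be conducted for the adverse effects measuring continuous outcome and for the categorical outcomes we will use Fisher's exact test". Safety p-values are left uncorrected so that harmful effects are more likely to be found.

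The section does not classify the 5-point score as continuous or categorical. It names no visit for the t-test, no form for time in the model, no per-patient summary and no severity cut.

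**The concern.** A t-test at one visit, or a group effect averaged over visits, compares mean levels. That suits pain, which is expected to shift and stay shifted. A stimulation side effect may instead appear at one or two sessions and resolve. A last-visit test will usually not contain it, and in an average over sessions it is diluted by the many sessions without it.

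The plan's own safety aim is at stake. Leaving p-values uncorrected helps little if the value being compared hardly moves when a patient has one bad session. Leaving the summary open also allows it to be chosen after the data are seen.

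**Working it through.** The plan states no power, event rate or sample size for adverse effects, so it has no figure to reproduce.

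**Number of ratings.** Visits 4b-13 give 10 stimulation sessions and Visits 14-19 give 6: 10 + 6 = 16. Section III gives 20 patients per arm.

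**Effect on a mean.** One session at 5 instead of 1 moves a patient's 16-session mean by 4/16 = 0.25; one at 4 instead of 1 moves it by 3/16 = 0.19. If 30% of the active arm is affected, the arm mean moves by 0.30 × 0.19 = 0.06 to 0.30 × 0.25 = 0.08 points.

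**Effect at one visit.** If the severe session falls at random, the expected number of active patients with it at the last session is 20 × 0.30/16 = 0.375.

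**Fisher's exact test on patients with any severe score (two-sided).** With k of 20 against 0 of 20, p = 2 × C(20,k)/C(40,k):
- k = 4: 2 × 4,845/91,390 = 0.106
- k = 5: 2 × 15,504/658,008 = 0.047

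Five affected patients are therefore needed when sham has none. With a true active rate of 30%, the chance of five or more among 20 is 76%. At 20% it is 37%, and at 40% it is 95%. If the sham rate is 5% instead of zero, power at 30% falls to 45%.

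**Simulation.** 20 per arm, 16 sessions, scores 1-5, two-sided 5%; 30% of active patients and no sham patients are given one added severe session at a random time. The rates, background scores and cut of 4 are all assumptions.
- Setting A: background score of 2 in 10% to 30% of sessions, with patients differing in propensity; severe score 4; 4,000 replicates; counted only when active is worse.
- Setting B: background from a latent normal scale with a patient effect, low or moderate level; severe score 4 or 5; 2,000 replicates.

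| Comparison | Setting A | Setting B |
|---|---|---|
| t-test, last session | 2-4% | 1-4% |
| t-test, session mean | 9-18% | 11-37% |
| t-test, worst score | 70-77% | not run |
| Rank test, worst score | not run | 39-43% |
| Fisher, any score of 4 or more | 75-78% | 69-75% |

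The session mean stands in for the time-averaged group effect of a mixed model; in a balanced random-intercept model the two are the same.

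**Other patterns.**
- Two severe sessions per affected patient: session mean 21-41% (A) and 26-62% (B), against worst-score t-test 71-77% (A) and Fisher 70-75% (B).
- 20% affected, one session (B): mean 9-21%, Fisher 34-35%. With two sessions and low background the two are level (36% and 35%).
- Group-by-visit interaction, severe scores at random sessions: 5-6%, which is chance level.
- Equal rates in both arms (A): harm-direction false positives 2-3% for the worst-score t-test and under 1% for Fisher.
- Recurrent mild effect, score 2 in 60% of active and 30% of sham sessions: session mean 93%, worst-score t-test about 25%. At 50% against 30%: 65% and 18%. With only 10% sham background the two are similar.

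**The case against.** Four objections have weight.

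1. **A reader might infer that the plan averages the scores over 16 sessions.** It does not say so. The t-test and mixed model apply to adverse effects measured as continuous, and the 5-point score is never named as one. VAMS, MMSE and Stroop reaction time, all repeated after stimulation, are other candidates. This stands: the defect is an unassigned outcome with one poor permitted reading.

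2. **A reader might infer that the plan, followed as written, would miss severe episodes in a quarter or more of active patients.** Fisher's exact test for categorical outcomes is in the same sentence. Applied per patient, 5/20 against 0/20 reaches p = 0.047. The inference holds only if that clause goes unused for these scores. However, no categorical adverse-effect outcome is defined per patient, so the route exists without an endpoint.

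3. **A reader might infer that scalp burns and scalp pain are being diluted.** The 5-point scale is attached to headache, neck pain, mood alterations and seizures. The other symptoms are asked about without a stated score, so the point is confined to scored items.

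4. **A reader might infer that a worst score should replace the mixed model.** The recurrent mild pattern argues against this, because the mean-level analysis is much stronger there.

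It can also be said that a group-by-visit model does not average over sessions. The form is not given, and such a model gained nothing for randomly timed harms; it could help if harms cluster at particular visits. Collecting seriousness, severity, duration and causality, and having a Medical Monitor, protect patients but do not define a comparison between arms.

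**Conclusion.** The point holds as a gap in the specification with a real consequence under one reading. The plan offers two routes for adverse effects, does not assign the 5-point scores to either, and defines no per-patient summary. If the scores go down the continuous route, a brief severe effect in 30% of active and no sham patients would be detected in roughly 2-4% of trials at the last session and 9-37% on the session mean, against about 70-78% for a per-patient any-severe comparison.

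These sizes rest wholly on assumed rates, background scores and cut. The gap narrows when severe sessions repeat or background is low, and absolute power falls for either method when fewer patients are affected or sham patients also have events. For the worst score itself the gain depends on the test: the t-test reached 70-77% in one setting, the rank test only 39-43% in the other. The any-severe count is the steadier of the two additions.

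No method makes 20 per arm sensitive to uncommon harm. Four of 20 against none gives p = 0.106. With none seen in 20, the one-sided 95% upper limit on the true rate is 1 - 0.05^(1/20) = 14%.

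**What to change.** In section IV, state which adverse-effect measures are continuous and which categorical, and name the visit for the t-test and the form of time in the model. Keep the planned t-test and mixed model. For each item scored on the 5-point scale, add:

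- (a) each patient's worst score over Visits 4b-19, compared between arms by a test named in advance;
- (b) the number of patients with any score at or above a level that the sponsor sets before unblinding, compared by the already planned Fisher's exact test, with the risk difference and its confidence interval.

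Report sessions attended by arm beside both. State that a non-significant result will not be read as absence of harm.

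The cost is a few lines of text, using data already collected. The downsides are additional uncorrected comparisons for each item and a maximum that depends on sessions attended, so early leavers have fewer chances of a high score. The attendance table lets a reader judge that.

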#### *Randomization:*

Once eligibility and consent have been approved and completed, after all baseline evaluations and immediately before the first stimulation session of Part II, stratified blocked randomization will occur using the randomized list generated by an automatic web-based randomization program ([www.randomization.com](http://www.randomization.com)). Randomization will be based on placebo effect above or below -17.3% according to preliminary data. A staff member who is not involved in any of the study procedures will be responsible for creating the randomization list and monitoring it during the study. Subjects will be randomly assigned to treatment or placebo groups in a 1:1 allocation ratio. We will use permuted blocks of variable sizes (4) in a random manner to minimize the risk of study staff guessing at the next allocation. Randomization order will be kept in sealed envelopes.

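### Fisher's exact test is conservative at 20 per arm and partly works against the plan's aim of making harm easier to detect; Boschloo's test is a cheap improvement for yes/no adverse effects

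*Combined protocol and SAP*

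**What the plan says.** Section IV (Biostatistical Analysis) plans to analyse continuous adverse-effect measures like the efficacy outcomes, and adds that "for the categorical outcomes we will use Fisher's exact test". For both kinds it says that "for safety analysis we will use uncorrected p-value to increase the likelihood of detecting detrimental adverse effects". Sensitivity to harm is therefore a stated aim, and the stated means is to omit a multiplicity correction. No alpha, sidedness, power or event rate is given for the safety tests. The only alpha in the section, 5%, belongs to the sample-size reasoning.

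Section III sets the arms as "active tDCS+active TUS (n=20) or sham tDCS+sham TUS (n=20 inactive transducers"), and the Randomization paragraph confirms 1:1 allocation. Section IV also says "All analyses will be conducted according to the principle of intention-to-treat", with single imputation. Description of Assessments lists the solicited symptoms ("headache, neck pain, scalp pain, scalp burns, tingling, skin redness, sleepiness, trouble concentrating, and acute mood change") and describes a questionnaire scored on a 5-point scale.

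**The concern.** A test whose true error rate is well below its nominal level gives up power. When a plan says that it wants harm to be easier to detect, a conservative test for harm pulls the other way. With 20 per arm, the number of possible 2x2 tables is small, so Fisher's test often cannot come close to 5%. At stake is whether a visible excess of a symptom under active stimulation, such as 8 patients against 2, is reported as non-significant when another test that also holds the 5% level would flag it.

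**Working it through.** The plan gives no safety error rate or power, so there is no figure of its own to reproduce.

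**Inputs.** From the documents: 20 per arm, Fisher's exact test, nine named symptoms. Assumed: a two-sided 5% level, one yes/no outcome per patient per symptom, and all event rates. Arms of 17 to 20 are also tried, because no dropout rate is given.

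**Method.** For arms of n and m patients with a and b events, take every possible table (21 x 21 = 441 at 20 v 20).

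- Fisher's p is the sum of the hypergeometric probabilities of all tables with the same total that are no more likely than the one observed. For 5 v 0: 2 x C(20,5)/C(40,5) = 2 x 15,504/658,008 = 0.047.
- Boschloo's p is the maximum, over a common event rate π, of the probability that Fisher's p is as small as the one observed. Because Fisher's test is valid, this maximum cannot exceed Fisher's own p.
- Rejection probability = sum over rejecting tables of Bin(a; n, π1) x Bin(b; m, π2). Setting π1 = π2 gives size; otherwise it gives power.

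**Size at 20 v 20.** Fisher: 0.19% at a common rate of 5%, 1.18% at 10%, 2.26% at 20%, 2.48% at 30%, with a maximum of 2.53% near 34% (and 66%). Boschloo: maximum 4.64%.

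**Power at 20 v 20 (active v sham).**

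| Rates | Fisher | Boschloo |
|---|---|---|
| 40% v 10% | 49% | 61% |
| 35% v 5% | 59% | 69% |
| 30% v 5% | 45% | 54% |
| 60% v 20% | 65% | 73% |
| 50% v 20% | 41% | 49% |
| 20% v 0% | 37% | 37% |
| 30% v 0% | 76% | 76% |

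The last two rows show no gain because, with no sham events, both tests need at least 5 active events: 5 v 0 is significant under both, and 4 v 0 under neither (Fisher 0.106, Boschloo 0.061).

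**Splits that cross 0.05 (Fisher to Boschloo).** 6 v 1: 0.091 to 0.046. 8 v 2: 0.065 to 0.039. 9 v 3: 0.082 to 0.042. 12 v 5: 0.054 to 0.030.

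**Other arm sizes, power at 40% v 10%.**

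| Active v sham n | Fisher max size | Fisher power | Boschloo power |
|---|---|---|---|
| 19 v 19 | 2.8% | 46% | 58% |
| 18 v 18 | 2.9% | 43% | 55% |
| 19 v 20 | 3.6% | 57.2% | 57.4% |
| 20 v 19 | 3.6% | 51.2% | 51.3% |
| 18 v 20 | 3.5% | 52% | 57% |
| 17 v 20 | 4.0% | 48% | 56% |
| 20 v 17 | 4.0% | 53.1% | 53.1% |

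Boschloo's test was never less powerful in any case tried.

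**What leaving out the correction achieves.** Fisher at 0.05 against Fisher at 0.05/9 = 0.0056 (Bonferroni over nine symptoms): 49% v 16% for 40% v 10%; 45% v 10% for 30% v 5%; 37% v 3% for 20% v 0%.

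**The case against.** A reader might infer that Fisher's test defeats the plan's aim, or that half of the alpha is always lost. The documents do not support either reading. The plan pursues its aim by not correcting for multiplicity, and that raises power several-fold even with Fisher's test. It promises no true size of 5%. The 2.5% peak belongs to exactly 20 v 20; losing one patient from one arm raises it to 3.6% and can remove almost all of the gain. Intention-to-treat with imputation would keep 20 v 20 if it is applied to adverse effects, but Description of Assessments lets any assessment other than VAS pain be skipped, so equal denominators for every symptom are not assured.

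Three further objections stand. Fisher's test is a standard and valid choice for sparse tables. For harms absent under sham, which may include the rare serious ones, Boschloo's test adds nothing. And it is a 2x2 test, while adverse effects are collected on a 5-point scale, so a blanket replacement would force severity to be dichotomised.

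It is also true that 20 per arm limits detection of harm more than the test does: Boschloo's test still reaches only 49% for 50% v 20%. And no decision in the plan hangs on a safety p-value crossing 0.05. These points limit the size of the matter. They do not remove it: dropping the correction and choosing the test are separate decisions, and the second gives back some of what the first gains.

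**Conclusion.** The point holds as a minor one. At the planned 20 v 20 and an assumed two-sided 5% level, Fisher's test has a maximum true size of about 2.5% against 4.6% for Boschloo's. Where sham events occur, this costs about 8 to 12 points of power under the rates assumed above. The gain ranges from that to nil at unequal arm sizes, and is nil when the sham rate is zero. The size of the gain rests on event rates and denominators that the documents do not give. That Boschloo's p never exceeds Fisher's, and that it holds the 5% level, does not. The plan's test is not an error; a better-matched one is available for yes/no outcomes.

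**What to change.** In the safety sentences of section IV:

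- For adverse effects analysed as yes/no per patient per symptom, replace Fisher's exact test with Boschloo's exact unconditional test at a stated two-sided 5% level, still uncorrected for multiplicity.
- Beside each p-value, report the risk difference with an exact confidence interval, and name the interval method.
- Keep Fisher's test, in its r x c form, for outcomes with more than two categories, such as the 5-point severity ratings, so that severity data are not dichotomised.
- State the denominator for each symptom, and whether missing adverse-effect data are imputed.

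The cost is a few sentences of wording, some extra code in whichever package is used, and a test that readers know less well. It needs no more patients or procedures. The benefit will depend on the final arm sizes.
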